## **2-6 Data Analysis**

Data was analyzed using IBM SPSS Statistics version 26. Descriptive statistics (mean, standard deviation, frequency, and percentage) were used to summarize demographic and clinical variables. The Kolmogorov-Smirnov test was applied to assess the normality of continuous variables, and due to non-normal distribution, non-parametric tests were used.

Bivariate analyses included Spearman's correlation coefficient to evaluate associations between psychological outcomes (depression, anxiety, stress) and continuous predictors such as sleep quality, cost, and number of children. The Kruskal-Wallis H test was employed to examine differences in distress levels across cancer stages.

Categorical associations were evaluated using Pearson's Chi-square test. Binary logistic regression analysis was conducted to identify predictors of severe anxiety. Additionally, multivariate linear regression models were constructed for each psychological outcome (PHQ-9, GAD-7, stress), and multicollinearity was assessed using the Variance Inflation Factor(VIF).

Receiver Operating Characteristic (ROC) curve analysis was used to assess the predictive accuracy of stress scores for severe anxiety, with Area Under the Curve (AUC) interpreted based on conventional thresholds. Conceptual path modeling was used to explore potential indirect relationships between stress and anxiety, mediated by sleep disturbance and impaired daily performance.

All tests were two-tailed, and a p-value of less than 0.05 was considered statistically significant.

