### 3 - Results

A total of 500 breast cancer patients were included in the final analysis. Descriptive statistics revealed a high prevalence of psychological distress within the sample, with elevated scores in depression, anxiety, and stress domains.

Spearman correlation analysis revealed strong positive associations between sleep difficulty and psychological outcomes: depression ( $r = 0.85$ ), anxiety ( $r = 0.77$ ), and stress ( $r = 0.85$ ), all statistically significant at  $p < 0.001$ . Use of sedatives was also significantly correlated with elevated distress scores ( $r > 0.90$  across models).

Kruskal-Wallis tests demonstrated statistically significant differences in mean ranks of depression, anxiety, and stress across cancer stages ( $p < 0.01$ ), with higher distress in patients with advanced-stage disease.

Multivariate linear regression identified the following as significant predictors of psychological distress:

- PHQ9\_Total:  $\beta = 0.42$ ,  $p < 0.001$
- Anger:  $\beta = 2.08$ ,  $p < 0.001$
- Cancer Stage:  $\beta = 0.92$ ,  $p = 0.0014$

Psychological support was not a significant predictor ( $p = 0.606$ ).

Binary logistic regression showed that PHQ9 and anger significantly predicted severe anxiety, with odds ratios of 1.32 and 1.27, respectively ( $p < 0.001$ ). Stage of disease also emerged as a significant factor in anxiety prediction.

Receiver Operating Characteristic (ROC) curve analysis yielded an Area Under the Curve (AUC) of 0.74 for stress in predicting severe anxiety, indicating a fair level of discriminative ability.

Finally, conceptual path analysis demonstrated that the relationship between stress and anxiety was primarily indirect, mediated through sleep disturbance and daily performance impairment. The direct path from stress to anxiety was negligible ( $r = -0.01$ ), suggesting a mediated mechanism of action.

**Table 1.** Descriptive Statistics of Study Variables

Variable	N	Minimum	Maximum	Mean	SD
Total Cost	500	80	34785	3721.69	4456.79
PHQ9_Total	500	1	27	17.99	6.11
GAD7_Total	500	1	21	12.79	3.81
Cancer Stage	500	0	4	2.52	1.09
Children	500	0	5	2.53	1.63
Metastatic	500	0	1	0.36	0.48
Stress Level	500	0	4	2.64	0.79

The descriptive characteristics of the study variables are presented in **Table 1**. Depression and anxiety scores were moderately high, while stress levels were also elevated. Treatment cost showed substantial variability across participants.

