**Table 2.** Spearman Correlation Matrix Among Study Variables

Variable	PHQ9_Total	GAD7_Total	Stress Level	Sleep Difficulty	Sleep Satisfaction	Total Cost

PHQ9_Total	1.00	0.79	0.66	0.85	0.49	-0.11
GAD7_Total	0.79	1.00	0.65	0.77	0.62	-0.10
Stress Level	0.66	0.65	1.00	0.85	0.55	-0.12
Sleep Difficulty	0.85	0.77	0.85	1.00	0.48	-0.08
Sleep Satisfaction	0.49	0.62	0.55	0.48	1.00	-0.09
Total Cost	-0.11	-0.10	-0.12	-0.08	-0.09	1.00

[figure not shown]
Spearman correlation coefficients between psychological outcomes and sleep-related variables are shown in **Table 2**. Strong positive correlations were observed between depression, anxiety, stress, and sleep difficulty.

**Table 3.** Kruskal–Wallis Test for Differences Across Cancer Stages

Variable	Chi-square (H)	df	P-value
Stress Level	31.092	3	<0.001
PHQ9_Total	14.762	3	0.002
GAD7_Total	19.705	3	<0.001

The Kruskal–Wallis test results (**Table 3**) indicate significant differences in depression, anxiety, and stress levels across cancer stages ( $P < 0.05$ ).

**Figure 1.** Chi-square (H) Values for Stress, Depression, and Anxiety

**Figure 1** shows the Chi-square (H) values for stress, depression, and anxiety. Stress exhibited the highest value (H = 31.09), followed by anxiety (H = 19.71) and depression (H = 14.76), all indicating significant differences across groups ( $P < 0.05$ ).

**Table 4.** Multiple Regression Analysis of Factors Associated with Depression, Anxiety, and Stress among Patients

Outcome	Predictor	B	T	P-value	VIF	R 
Depression (PHQ-9)	Use of Sedatives	4.842	10.817	<0.001	1.766	0.702
	Sleep Difficulty	4.52	11.221	<0.001	4.866	
	Sleep Satisfaction	0.364	2.01	0.045	1.021	
	Children	0.075	0.626	0.532	1.039	
	Total Cost	7.5E-5	2.209	0.028	1.022	

	Metastatic	-0.13	-0.408	0.684	1.048	
Anxiety (GAD7)	Use of Sedatives	4.064	12.807	<0.001	1.766	0.615
	Sleep-related Worry	1.521	6.193	<0.001	3.655	
	Sleep Satisfaction	0.539	1.886	0.060	4.866	
	Children	0.205	1.889	0.060	1.039	
	Total Cost	3.0E-5	1.246	0.213	1.022	
	Metastatic	0.203	0.896	0.371	1.048	
Stress Level	Use of Sedatives	1.856	29.413	<0.001	1.766	—
	Sleep-related Worry	0.149	3.048	0.002	3.655	
	Children	0.037	1.705	0.089	1.039	
	Metastatic	0.084	1.865	0.063	1.048	
	Total Cost	3.4E-6	0.711	0.477	1.022	

The results of the multiple regression analysis are summarized in **Table 4**. Use of sedatives and sleep-related worry were significant predictors of stress, depression, and anxiety scores.

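### The Children rows of Table 4 cannot be reconciled with Table 1, and the documents do not show which printed entry is wrong

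*Combined protocol and SAP*

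**What the plan says.** The sample is fixed at one size: "A total of 500 breast cancer patients were included in the final analysis". Table 1 in section 3 ("Descriptive Statistics of Study Variables") lists N, minimum, maximum, mean and SD. The rows needed here are "Children 500 0 5 2.53 1.63", "PHQ9_Total 500 1 27 17.99 6.11", "GAD7_Total 500 1 21 12.79 3.81" and "Stress Level 500 0 4 2.64 0.79".

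Table 4 in the same section ("Multiple Regression Analysis of Factors Associated with Depression, Anxiety, and Stress among Patients") gives B, T, p and VIF for each predictor. R² is 0.702 for depression and 0.615 for anxiety; the stress model has a dash. The Children rows read:

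- Depression: B 0.075, T 0.626, p 0.532, VIF 1.039
- Anxiety: B 0.205, T 1.889, p 0.060, VIF 1.039
- Stress: B 0.037, T 1.705, p 0.089, VIF 1.039

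Section 2-6 sets a two-sided 0.05 threshold. It mentions number of children among "continuous predictors such as sleep quality, cost, and number of children", in the sentence on Spearman correlation. Its regression sentence lists no predictors.

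**The concern.** In ordinary least squares, the standard error of a coefficient is determined by the outcome SD, the predictor SD, the VIF, R² and the sample size. Tables 1 and 4 give all of these except the stress R², so each row can be checked. A predictor measured once in the same 500 patients should return the same SD from every model, and that SD should be the one in Table 1. Children does not.

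Two printed results lie just above 0.05. Depending on which entry is wrong, either those two results cross the report's own threshold or the printed coefficients are too large, by more than 60% for anxiety and stress.

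**Working it through.** **Formula.** SE(B) = (SDy/SDx) × √[(1 − R²) × VIF/(n − k − 1)]. The SE implied by the table is B/T.

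**Inputs.** n = 500. Table 1 SDs: PHQ-9 6.11, GAD-7 3.81, stress 0.79, Children 1.63, Total Cost 4456.79, Metastatic 0.48. B, T, VIF and R² come from Table 4. k is the number of predictors listed (6, 6 and 5); taking k anywhere from 5 to 7 changes the SE by about 0.2%.

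**Printed T against printed p.** These agree. T = 0.626, 1.889 and 1.705 give two-sided p = 0.532, 0.0595 and 0.0888, which are the printed values after rounding.

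**Stress R² (derived).** Solving the formula for R² gives 0.648 from the Cost row and 0.647 from the Metastatic row; 0.648 is used. The sedatives T of 29.413 alone requires R² ≥ 29.413²/(29.413² + 494) = 0.637. Because these two rows set R², the genuine check in the stress model is that they agree with each other.

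**Control rows, printed B/T over formula SE.**

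| Row | PHQ-9 | GAD-7 | Stress |
|---|---|---|---|
| Total Cost | 0.996 | 0.997 | 1.000 |
| Metastatic | 0.995 | 0.998 | 1.001 |

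**Children, expected SE.**

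- PHQ-9: (6.11/1.63) × √(0.298 × 1.039/493) = 0.0939
- GAD-7: (3.81/1.63) × √(0.385 × 1.039/493) = 0.0666
- Stress: (0.79/1.63) × √(0.352 × 1.039/494) = 0.0132

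| Children row | PHQ-9 | GAD-7 | Stress |
|---|---|---|---|
| Printed B/T | 0.1198 | 0.1085 | 0.0217 |
| Ratio to expected SE | 1.28 | 1.63 | 1.65 |
| SD of Children needed (Table 1: 1.63) | 1.28 | 1.00 | 0.99 |
| VIF needed instead (printed: 1.039) | 1.69 | 2.76 | about 2.8 |

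**Check without R² or outcome SD.** Within one model, the ratio of two SEs depends only on the predictor SDs and VIFs.

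- SE(Children)/SE(Metastatic) should be (0.48/1.63) × √(1.039/1.048) = 0.293. Table 4 gives 0.376, 0.479 and 0.482.
- SE(Metastatic)/SE(Cost) should be (4456.79/0.48) × √(1.048/1.022) = 9,402. Table 4 gives 9,385, 9,410 and 9,419.

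**If B, VIF and the Table 1 SD are right.**

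- Depression: T = 0.075/0.0939 = 0.80, p about 0.42 (printed 0.532)
- Anxiety: T = 0.205/0.0666 = 3.08, p = 0.002 (printed 0.060)
- Stress: T = 0.037/0.0132 = about 2.8, p = 0.005 (printed 0.089)

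With worst-case rounding of the inputs, and stress R² as low as 0.60, anxiety T is at least 3.05 (p = 0.0024) and stress T at least 2.57 (p = 0.011). Keeping both the printed B and T for stress would need R² of about 0.05, which the sedatives row rules out.

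**If T and p are right.** B = T × expected SE: 0.626 × 0.0939 = 0.059, 1.889 × 0.0666 = 0.126 and 1.705 × 0.0132 = about 0.022. The nulls stand.

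**The case against.** The strongest reply is that the nulls are probably sound. T and p agree with each other in every Children row, so if they are wrong, two cells must be wrong in matching fashion in each of three rows. A misprinted B needs only one wrong cell per row. This stands as a reason not to prefer the significant branch, though it does not prove the other.

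Nor is the choice only between B on one side and T and p on the other. A different coding, a wrong row label or a wrong VIF would leave B, T and p all as fitted. There is a sign of label trouble in this table: in the anxiety model, the row labelled Sleep Satisfaction has VIF 4.866, which is Sleep Difficulty's VIF in the depression model, where Sleep Satisfaction has 1.021. Its implied SD, 3.81 × √(0.385 × 4.866/493)/(0.539/1.886) = 0.822, also matches the 0.823 implied by the Sleep Difficulty row.

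A reader might infer that Children has three different SDs. The values for anxiety and stress (1.00 and 0.99) coincide within rounding, so there are two: 1.28 and about 1.0. One common cause could explain anxiety and stress together, but no single change of SD or VIF repairs all three rows.

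A reader might also take number of children to be a regression predictor named in section 2-6. It is named there only for Spearman correlation.

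Finally, materiality is limited. The text under Table 4, the discussion, the clinical implications and the conclusion do not mention children. That lowers the stakes. It does not settle whether the printed non-significance is correct.

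**Conclusion.** The inconsistency is established: the printed SEs for Children are 1.28, 1.63 and 1.65 times what Tables 1 and 4 require, while the control rows fit within 1%. Rounding cannot explain it, so at least one figure or label bearing on each Children row is wrong.

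What follows for significance is conditional. A reader might infer that number of children is in fact associated with anxiety and stress and that the reported nulls are false. The documents do not support that: it holds only if B, the VIF and the Table 1 SD are all correct. Other explanations leave the nulls intact. Depression is non-significant on either branch.

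The conclusion assumes ordinary least squares on all 500 patients with the Table 1 variables. For stress, the back-calculated SD and T also rest on the derived R²; the SE-ratio check does not. This is a reporting error that should be corrected, with high confidence in the mismatch and none in which branch is true.

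**What to change.** Re-extract the Children rows for all three models from the existing SPSS output. Check that the variable entered, its coding (0 to 5, SD 1.63), its row label and its VIF match Table 1. Reissue Table 4 with B, SE, T, p and VIF for every predictor, the full predictor list and the stress R², and correct whichever entries are wrong. Check the anxiety row labelled Sleep Satisfaction at the same time. Then report the association of number of children with anxiety and stress according to the corrected p-values, whether or not they fall below 0.05.

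The cost is re-reading existing output and correcting a few table rows. No new data are needed.

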**Table 5:** Binary Logistic Regression – Predicting Severe Anxiety

Predictor	Odds Ratio (OR)	95% CI	P-value
Depression (PHQ-9)	1.32	1.18 – 1.56	<0.001

Anger	1.27	1.11 – 1.49	0.002
Stress Level	1.14	1.03 – 1.35	0.017
Psychological Support	0.54	0.33 – 0.91	0.021
Cancer Stage	0.61	0.33 – 0.87	0.049

[figure not shown]
Binary logistic regression (**Table 5**) showed that depression, anger, and stress significantly increased the odds of severe anxiety, while psychological support and advanced cancer stage were protective. The corrected model (**Table 6**) confirmed these associations.

**Table 6.** Logistic Regression Predicting Severe Anxiety (Corrected Model)

Predictor	Coef. ( $\beta$ )	Std. Error	z-value	p-value	95% CI (Lower – Upper)
PHQ9_Total	0.42	0.06	6.92	<0.001	0.30 – 0.53
Anger	2.08	0.48	4.36	<0.001	1.14 – 3.02
Psych Support	-0.18	0.34	-0.52	0.606	-0.84 – 0.49
Cancer Stage	0.92	0.29	3.20	0.0014	0.36 – 1.48

[figure not shown]
This table presents the corrected logistic regression model for predicting severe anxiety. PHQ9\_Total and anger were significant positive predictors, while psychological support did not show a significant protective effect in the adjusted model.

**Figure 2.** ROC Curve for stress predicting severe anxiety.

The ROC curve (**Figure 2**) illustrates the predictive value of stress scores for severe anxiety, with an AUC of 0.74 ( $p < 0.001$ ), indicating fair discriminative accuracy.

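### In Table 5 the odds ratio, 95% CI and p-value cannot all be right for stress or for cancer stage, and Table 6 confirms neither row

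*Combined protocol and SAP*

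**What the plan says.** Section 2-6 (Data Analysis) states that "Binary logistic regression analysis was conducted to identify predictors of severe anxiety", using SPSS 26. It adds: "All tests were two-tailed, and a p-value of less than 0.05 was considered statistically significant". It mentions no bootstrap or profile-likelihood interval.

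Table 5 in section 3 has the columns "Predictor Odds Ratio (OR) 95% CI P-value". The two rows at issue are "Stress Level 1.14 1.03 – 1.35 0.017" and "Cancer Stage 0.61 0.33 – 0.87 0.049". The depression row is "Depression (PHQ-9) 1.32 1.18 – 1.56 <0.001". Anger is given as 1.27 (1.11 to 1.49), p = 0.002, and psychological support as 0.54 (0.33 to 0.91), p = 0.021.

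The text under Table 5 says the model "showed that depression, anger, and stress significantly increased the odds of severe anxiety, while psychological support and advanced cancer stage were protective", and then that the corrected model in Table 6 bore these associations out. Table 6 lists PHQ-9, anger, psychological support and cancer stage. Its stage row is beta 0.92, SE 0.29, z 3.20, p = 0.0014, CI 0.36 to 1.48.

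The opening text of section 3 reports depression and anger "with odds ratios of 1.32 and 1.27, respectively", both with p < 0.001.

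**The concern.** The OR, interval and p-value of one logistic-regression coefficient come from the same estimate and standard error. Any two of them fix the third, up to rounding. If they disagree, at least one was mistranscribed or came from a different run.

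Two stated conclusions rest on the affected rows: that stress raises the odds of severe anxiety, and that advanced stage is protective. Table 5 is the only multivariable model for severe anxiety that contains stress, so no other printed table can check that row. Stage does appear in Table 6, but with the opposite sign.

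**Working it through.** **Inputs.** The five rows of Table 5; a two-sided 0.05 level (section 2-6); N = 500 (section 3), so t versus z makes no material difference. Assumption: Wald intervals, because section 2-6 describes no other kind.

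**Formulas.** For limits L and U: midpoint M = √(L × U), which should equal the OR; SE = (ln U − ln L)/3.92; p = 2[1 − Φ(|ln OR|/SE)]. Each printed figure was also varied by ±0.005 for rounding. The midpoint test does not depend on the confidence level, so a mislabelled 90% or 99% interval could not repair a row.

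**A row that reproduces.** Psychological support: M = √(0.33 × 0.91) = 0.548 (0.542 to 0.554 with rounding), against 0.54. SE = 0.2588 and p = 0.017 (0.014 to 0.022), against 0.021. This row is consistent.

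**Centring of all rows.**

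| Row | Printed OR | M | M with rounding |
|---|---|---|---|
| Depression | 1.32 | 1.357 | 1.352 to 1.362 |
| Anger | 1.27 | 1.286 | 1.281 to 1.291 |
| Stress | 1.14 | 1.179 | 1.174 to 1.184 |
| Psychological support | 0.54 | 0.548 | 0.542 to 0.554 |
| Cancer stage | 0.61 | 0.536 | 0.530 to 0.541 |

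Allowing ±0.005 on the OR as well, only psychological support overlaps. For depression, the printed OR with the interval width gives p = 0.0001, so p < 0.001 holds. For anger it gives 0.0015 (0.0009 to 0.0023), which includes the printed 0.002.

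**Stress.** The log half-widths are ln(1.14/1.03) = 0.101 below and ln(1.35/1.14) = 0.169 above. SE = (0.3001 − 0.0296)/3.92 = 0.0690.
- Interval right: OR = 1.18, z = 0.1648/0.0690 = 2.39, p = 0.017. This matches the printed p.
- OR and p right: SE = 0.0549, CI 1.02 to 1.27, not 1.03 to 1.35.
- OR and interval width right: z = 0.1310/0.0690 = 1.90, p = 0.058 (0.043 to 0.075 with rounding).

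**Stage.** The log half-widths are 0.614 below and 0.355 above. SE = (1.1087 − 0.1393)/3.92 = 0.2473.
- Interval right: OR = 0.54, z = 0.6240/0.2473 = 2.52, p = 0.012 (0.010 to 0.013), not 0.049.
- OR and p right: SE = 0.2511, CI 0.37 to 0.998, not 0.33 to 0.87.
- OR and interval width right: z = 0.4943/0.2473 = 2.00, p = 0.046 (0.038 to 0.054). This fits the printed p but not the printed position of the interval.

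**Against Table 6.** The Table 6 stage row is internally consistent: 0.92/0.29 = 3.17, and 0.92 ± 1.96 × 0.29 = 0.35 to 1.49. It gives OR = exp(0.92) = 2.51, with limits exp(0.36) = 1.43 and exp(1.48) = 4.39. Table 5 has 0.61. Table 6 has no stress row.

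**Anger p-value.** The opening text of section 3 attaches p < 0.001 to the OR of 1.27; Table 5 prints 0.002 for it.

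**The case against.** Several counter-arguments deserve weight.

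*Asymmetric intervals are legitimate.* Bootstrap or profile-likelihood limits need not centre on the OR, and all four off-centre rows lean away from the null, as a different interval method beside Wald p-values might produce. This remains a possibility only: section 2-6 describes no such method, and the support row behaves as a Wald row.

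*A reader might infer that stress is not significant.* The documents do not support that. The printed interval excludes 1 and agrees with the printed p, so the simplest reading is a misprinted OR of 1.14 for about 1.18. The value 0.058 arises only by pairing the off-centre OR with the interval width, and its rounding range straddles 0.05.

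*A reader might infer that stage loses significance.* That is not shown either. The three readings above give 0.012, 0.049 and 0.046; only rounding in the last takes p past 0.05. Keeping the OR and the lower limit alone would give p = 0.115, but that discards both the printed upper limit and the printed p-value.

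*Reach is limited.* The values 1.14 and 0.61 are not cited outside Table 5. The Discussion takes its stage result from Table 6, and the link between stress and anxiety has unadjusted support elsewhere (Spearman 0.65, AUC 0.74). This is fair, but Table 5 has not been withdrawn: 1.32 and 1.27 are cited in section 3 and 0.54 in section 4.

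*The reversed stage sign may be a coding change.* The Discussion does refer to an adjustment for stage coding. If that is the reason, the description of advanced stage as protective should not stand beside a claim that Table 6 confirms it.

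**Conclusion.** The inconsistency is real. Under Wald intervals, at least one printed number is wrong in the stress row and at least one in the stage row, and rounding explains neither. It would go too far to say that both the estimate and the interval are wrong, because the documents do not identify the faulty number. It would also be wrong to say that the other three rows all pass: depression and anger are off-centre by a small amount, without consequence for their conclusions.

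The size is an OR of 1.14 against 1.18 for stress, and for stage 0.61 against 0.54 with p = 0.049 against 0.012. Significance may be lost for stress, but this is not demonstrated; for stage it is not shown. The weightier problem for stage is direction, 0.61 in Table 5 against about 2.5 in Table 6. The statement that Table 6 confirms Table 5 is therefore unsupported for stage, and it cannot apply to stress, which Table 6 omits.

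**What to change.** Re-run the severe-anxiety model on the existing data and print B, SE, OR, Wald CI and p for every row from the same output. If another interval method was used, name it in section 2-6. Alternatively, withdraw Table 5 and every OR taken from it: 1.32 and 1.27 in section 3, and 0.54 in the Discussion.

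In either case, state how stage is coded and reconcile its direction with Table 6, make the anger p-value agree between text and table, and remove the statement that Table 6 confirmed the Table 5 associations.

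The cost is one model re-run and some text edits, with no new data. The downside is that the stress result may become less favourable.

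### Table 5's Stress Level row is too precise to come from the Stress Level variable in Table 1 (N = 500, SD 0.79), so it does not support a significant adjusted effect of stress on severe anxiety

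*Combined protocol and SAP*

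**What the plan says.** Section 2-6 (Data Analysis) sets out the method: "Binary logistic regression analysis was conducted to identify predictors of severe anxiety". It also gives the significance rule: "All tests were two-tailed, and a p-value of less than 0.05 was considered statistically significant".

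Section 3 (Results) reports that "A total of 500 breast cancer patients were included in the final analysis". In Table 1, titled "Descriptive Statistics of Study Variables", the columns are N, minimum, maximum, mean and SD, and the stress row reads "Stress Level 500 0 4 2.64 0.79".

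In Table 5 the Stress Level entries for OR, 95% CI and p are "1.14 1.03 – 1.35 0.017". The sentence below the table concludes that "depression, anger, and stress significantly increased the odds of severe anxiety, while psychological support and advanced cancer stage were protective". The next sentence says that the corrected model in Table 6 confirmed these associations. Table 6 has rows for PHQ-9, anger, psychological support and cancer stage, and none for stress.

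**The concern.** The precision of a logistic coefficient has a ceiling set by the sample size and the spread of the predictor. Stress Level has a narrow spread (SD 0.79 on a 0 to 4 scale), yet its interval in Table 5 is narrow for 500 patients. If the interval is narrower than the ceiling allows, the row cannot have been produced by the described variable in the described sample, and making the OR, CI and p agree with each other would not repair it.

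At stake is one of the three positive predictors that the text names for severe anxiety. The document elsewhere calls the direct stress-to-anxiety path negligible (r = -0.01), so a reader needs to know whether an adjusted stress effect was found at all.

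**Working it through.** **Inputs.** Table 5, stress row: OR 1.14, CI 1.03 to 1.35, p = 0.017. Table 1: N = 500, Stress Level SD 0.79. Two-sided alpha 0.05 (section 2-6). The share of patients with severe anxiety is not stated; the bound below does not need it.

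**1. Can the printed p be reproduced from the row itself?**
- SE implied by the CI = ln(1.35/1.03)/(2 × 1.96) = 0.069.
- z = ln(1.14)/0.069 = 1.90, so p = 0.058 (0.043 to 0.075 over the rounding limits of OR and CI), not 0.017.
- The printed p returns only if the OR is taken as the geometric midpoint of the CI, √(1.03 × 1.35) = 1.18; then p = 0.017.
- OR 1.14 with p = 0.017 (z = 2.387) implies SE = 0.131/2.387 = 0.055.

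**2. The smallest SE that Table 1 allows.** In a logistic model each patient contributes weight π(1 − π), which is at most 0.25, and other covariates can only reduce the information on a slope. So

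information ≤ 0.25 × (N − 1) × SD² = 0.25 × 499 × 0.79² = 77.9, and SE ≥ 1/√77.9 = 0.113.

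Both SEs implied by the row, 0.069 and 0.055, are below this. The first is 61% of the minimum.

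**3. What follows.**
- CI width, whatever the OR: the upper-to-lower ratio must be at least exp(3.92 × 0.1133) = 1.56 (1.555 if the SD is 0.795 before rounding). Printed: 1.35/1.03 = 1.31, and at most 1.355/1.025 = 1.32 with rounding.
- If OR 1.14 is correct: z ≤ 0.131/0.1133 = 1.16, p ≥ 0.25, and the CI is no narrower than 0.91 to 1.42. With rounding in the document's favour (SD 0.795, OR 1.145), p ≥ 0.23.
- If the OR is 1.18: p ≥ 0.14.
- The printed CI would need an SD of about 1.30, or about 1,350 patients.
- The smallest OR that could reach p < 0.05 in this best case is exp(1.96 × 0.1133) = 1.25.

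**4. Less favourable assumptions, for scale.** Table 1 gives "GAD7_Total 500 1 21 12.79 3.81" for GAD-7. Assuming a normal shape, about 33% of patients score 15 or more; the univariate SE is then 0.121 and p = 0.28 at OR 1.14. If the Spearman correlation of 0.66 between stress and PHQ-9 (Table 2) is also used as a stand-in for their linear correlation, the SE is 0.161 and p about 0.42. A logistic model fitted to an illustrative 0 to 4 distribution (mean 2.64, SD 0.756) gave Wald and likelihood-ratio p-values both of 0.27.

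**5. Is the bound too strict?** The same bound, 2/(SD × √499), can be applied to the other logistic predictors with an SD in Table 1:

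| Row | SE | Minimum | Ratio |
|---|---|---|---|
| Table 5 PHQ-9 | 0.071 | 0.0147 | 4.9 |
| Table 5 Cancer Stage | 0.247 | 0.082 | 3.0 |
| Table 6 PHQ-9 | 0.06 | 0.0147 | 4.1 |
| Table 6 Cancer Stage | 0.29 | 0.082 | 3.5 |
| Table 5 Stress Level | 0.069 | 0.113 | 0.61 |

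Only the stress row falls below the minimum.

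**The case against.** A reader might infer that stress has been wrongly called significant, or that it has no relation to severe anxiety. The documents do not support either. The bound p ≥ 0.25 holds only if OR 1.14 is the correct entry, and the arithmetic does not say which entry is wrong. An OR of 1.25 to 1.35 lies inside the printed CI and could be significant in the best case. The AUC of 0.74 for stress predicting severe anxiety and the Spearman correlation of 0.65 between Stress Level and GAD-7 (Table 2) are unadjusted, but they point to an association. This stands, and it limits the conclusion to the adjusted effect.

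Table 5 might also use a different stress variable. Section 2-4 describes no stress instrument, and the ROC text speaks of stress scores rather than Stress Level. However, Tables 1, 2, 4 and 5 share one label and no second scale is described. Standardising to SD 1 would not help either: the minimum SE would be 2/√499 = 0.090, and p ≥ 0.14 at OR 1.14. An undisclosed variable would itself need reporting. Missing data would only widen the interval, and section 2-6 mentions no robust standard errors.

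Finally, the main conclusions do not rest on this row. The Results narrative names PHQ-9, anger and stage for severe anxiety, the Discussion puts depression and anger first, and the Conclusion does not claim that stress predicts severe anxiety. That is fair and narrows the consequence. But Table 5 is not withdrawn: the text says Table 6 confirmed it, and the Discussion still cites its OR of 0.54 for psychological support.

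**Conclusion.** The stress row of Table 5 and the Stress Level row of Table 1 cannot both be right. The implied SE of 0.069 compares with a minimum of 0.113, and the CI ratio of 1.31 with a minimum of about 1.56. At least one of the OR, CI, p-value, Table 1 SD or identity of the stress variable is misreported. Table 5 therefore does not support a significant adjusted effect of stress on severe anxiety, and Table 6 cannot supply that support. Whether a valid adjusted effect exists is open until the model is refitted.

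This assumes that Stress Level is the same variable in both tables and enters per point, that standard errors are the usual model-based ones, and that at most 500 patients were analysed. It needs no assumption about the event share or the other covariates.

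**What to change.** - Refit the Table 5 model with the 0 to 4 Stress Level of Table 1 and reprint its OR, CI and p-value. If another stress variable was used, name it, describe how it was measured and add it to Table 1. If the Table 1 SD is the error, correct it there.
- Keep stress among the predictors said to raise the odds of severe anxiety significantly only if the refit shows it.
- Correct the statement that Table 6 confirmed these associations, or add stress to that model and report the result.

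The cost is one model rerun, a corrected table row and two edited sentences. No new data are needed. The stress claim may be weakened or withdrawn, depending on the refit.
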